## **Study Protocol**

A total of 60 lower impacted wisdom teeth were extracted from 30 patients participating in the study. The study was conducted as a randomized controlled trial (closed envelope method). One mucosal or bone retention fully impacted wisdom tooth was extracted from each patient at a time. The tooth extraction on the other side of the same patient was performed 3 weeks later after postoperative complications were eliminated and the extraction site wound healed and the mouth opening returned to its previous value. Patients whose extraction sites did not heal were not included in the study. The wound closure technique to be applied to the tooth to be extracted was randomly decided by the closed envelope method. The side to which suture was applied after tooth extraction was determined as the control group, and the side to which cyanoacrylate tissue adhesive (Periacryl 90) was applied was determined as the experimental group.

All operations were performed by the same dentist. In Group 1, a full thickness gingival flap was lifted to reach the first tooth to be extracted and after the procedure, the gingiva was sutured with silk in the starting position, while in Group 2, the lifted full thickness flap of the second tooth to be extracted was brought to the starting position and tissue adhesive (Periacryl 90) was applied.

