## **Surgical Technique and Application**

The patients in the study were operated on by the same physician in the local operating room environment at the XXX University, Faculty of Dentistry, Department of Oral, Dental and Maxillofacial Surgery, in accordance with the rules of asepsis and antisepsis. It was planned to extract one mandibular wisdom tooth with mucosal or bone retention from each patient at a time. The tooth extraction on the other side was performed after the postoperative complications were eliminated and the extraction site wound healed and the mouth opening was restored. The wound closure technique to be used in the tooth extraction was determined by the closed envelope method and the surgical procedure was completed using a different technique in the other tooth extraction.

The oral cavity was cleaned with an antiseptic solution before surgery and the surgical field was prepared in accordance with aseptic conditions. Demographic data, preoperative mouth opening, facial landmark measurements, data regarding the impacted tooth and the operation were recorded in the anamnesis form. Inferior alveolar block anesthesia was performed with direct technique using 3 cc articaine hydrochloride 80 mg- Epinephrine 0.010 mg/ampule (Maxicaine VEM, Turkey) with 27 gauge dental syringes. The same equipment and local anesthetic were used for buccal anesthesia. Winter type envelope flap was preferred using a scalpel tip of No. 15 in the surgeries. Following the incision, the full thickness flap was lifted to reach the extraction area. In teeth with bone retention, the bone was lifted with a 1.6 mm diameter steel rond bur, fissure bur, surgical micromotor operating at 40,000 rpm and serum irrigation, and then the teeth were exposed. Then, the teeth were extracted with the help of a bein elevator. Irrigation was performed with physiological serum to prevent the heat generated during the bone removal procedure from damaging the living tissues. Teeth that could not be extracted in one piece due to their position were divided and extracted with a surgical micromotor. After extraction, the dental follicle was removed from the alveolar region with the help of curettes and clamps. The extraction socket and the bottom of the

mucoperiosteal flap were irrigated with plenty of physiological serum to remove bone particles and tissue residues.

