## **Statistical Analyses**

While evaluating the findings obtained in the study, NCSS (Number Cruncher Statistical System) 2020 Statistical Software (NCSS LLC, Kaysville, Utah, USA) program was used for statistical analyses. While evaluating the study data, quantitative variables were shown with mean, standard deviation, median, min and max values, and qualitative variables were shown with descriptive statistical methods such as frequency and percentage. Shapiro Wilks test and Box Plot graphics were used to evaluate the conformity of the data to normal distribution.

Student t-test was used in quantitative two-group evaluations showing normal distribution.

Mann Whitney-U test was used in the evaluations of variables not showing normal distribution according to two groups.

In intra-group comparisons according to follow-ups, Paired Samples test and Repeated Measures test were used in post hoc comparisons of variables showing normal distribution, and Bonferroni test was used.

Pearson Chi-Square test, Fisher's Exact test and Fisher Freeman Halton test were used in the comparison of qualitative data.

The results were evaluated at a 95% confidence interval and significance was at  $p < 0.05$ .

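### A patient's two teeth need not share the same retention type, and the planned tests do not adjust for it, so the closure comparison may lose precision

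*Combined protocol and SAP*

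**What the plan says.** The Study Protocol section gives the sample: "A total of 60 lower impacted wisdom teeth were extracted from 30 patients participating in the study". One side of each patient is closed with suture and the other with tissue adhesive. Retention is stated per tooth: "One mucosal or bone retention fully impacted wisdom tooth was extracted from each patient at a time". The Surgical Technique and Application section repeats this: "It was planned to extract one mandibular wisdom tooth with mucosal or bone retention from each patient at a time". Neither statement asks that the two sides be alike, and the closed-envelope draw is described without any balancing on retention.

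Retention changes the operation: "In teeth with bone retention, the bone was lifted with a 1.6 mm diameter steel rond bur, fissure bur, surgical micromotor". No such step is described for mucosally retained teeth. Sectioning is a further difference, decided by position: "Teeth that could not be extracted in one piece due to their position were divided and extracted with a surgical micromotor".

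On records, the same section says that "data regarding the impacted tooth and the operation were recorded in the anamnesis form". It does not name retention type.

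Under Statistical Analyses, "Student t-test was used in quantitative two-group evaluations showing normal distribution". Mann-Whitney U covers non-normal variables, and chi-square and Fisher-type tests cover categorical ones. Paired and repeated-measures tests are named only for comparisons within a group over follow-up. No covariate, stratum or subgroup is mentioned.

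**The concern.** Using each patient as his or her own control cancels what the two sides have in common. It does not cancel a factor that differs between them. If one tooth is bone-retained and the other mucosally retained, the effect of drilling on swelling and mouth opening falls entirely inside that patient's suture-minus-adhesive difference.

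Across patients, a fair draw places the bone-retained tooth under suture about as often as under adhesive. With 30 patients and no balancing, the split can be uneven, and the closure estimate then moves in that direction. Even an exactly even split leaves extra scatter in the differences, which an unadjusted comparison carries as noise. Retention belongs to the tooth before closure, so closure cannot affect it and it is a legitimate covariate.

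**Working it through.** **Inputs from the documents.** 30 patients with two teeth each: 30 × 2 = 60, which agrees with the stated total. There is no power, effect size, SD or sample-size calculation to reproduce.

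**Assumptions (not in the documents).** *m* = number of patients with mixed retention, taken as 6, 10 or 15. *e* = bone-versus-mucosal effect δ divided by σ, the SD of the within-patient difference in concordant pairs, taken as 0.5 to 1.0. The draw is fair.

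**Model.** The suture-minus-adhesive difference for a patient is τ + δx + error. Here x is 0 in a concordant pair, and +1 or −1 with equal probability in a mixed pair.

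**Chance shift of the closure estimate.** If *k* of the *m* mixed patients have the bone-retained tooth under suture, the estimate shifts by δ(2k − m)/30. The SD of this shift is δ√m/30:

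- m = 6: √6/30 = 0.082 δ
- m = 10: √10/30 = 0.105 δ
- m = 15: √15/30 = 0.129 δ

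For m = 10, a split of 7/3 or worse in either direction has probability 352/1024 = 0.344 and shifts the estimate by at least 4/30 = 0.133 δ. A split of 8/2 or worse has probability 112/1024 = 0.109 and shifts it by at least 6/30 = 0.20 δ. On the scale of σ, the 7/3 shift is 0.133 × 0.5 = 0.07 to 0.133 × 1.0 = 0.13 SD.

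**Loss of precision.** The variance of an unadjusted paired difference is multiplied by 1 + e²m/30, and the standard error by its square root:

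| m | e | Variance factor | SE factor |
|---|---|---|---|
| 6 | 0.5 | 1.050 | 1.025 |
| 6 | 1.0 | 1.200 | 1.095 |
| 10 | 0.5 | 1.083 | 1.041 |
| 10 | 1.0 | 1.333 | 1.155 |
| 15 | 0.5 | 1.125 | 1.061 |
| 15 | 1.0 | 1.500 | 1.225 |

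For m = 10, the standard error goes from 1/√30 = 0.183 SD to 0.183 × 1.041 = 0.190 SD (about 4% more) or 0.183 × 1.155 = 0.211 SD (about 15% more).

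**In terms of power.** Suppose 30 concordant pairs gave 80% power at two-sided 0.05, so that the standardized effect is 1.960 + 0.842 = 2.802. For m = 10 the unadjusted power is Φ(2.802/1.041 − 1.960) = 0.77 at e = 0.5, and Φ(2.802/1.155 − 1.960) = 0.68 at e = 1.0. Over a wider range, from 10% mixed pairs with e = 0.5 to 50% mixed pairs with e = 1.0, power runs from 79% down to 63%.

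These figures describe a paired difference, which the plan does not name as its comparison of techniques. They measure what retention adds to a within-patient analysis, not how the listed independent-groups tests behave.

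**The case against.** The strongest reply is that randomization already deals with this. Under a fair draw, mixed pairs cause no bias, and a standard error computed from within-patient differences already contains the extra variation. Any prognostic factor in any randomized trial can be imbalanced by chance. This stands and limits the point to precision. It does not remove the point, because adjusting for a strong tooth-level factor is a cheap way to recover that precision.

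Second, mixed pairs are only possible, not shown. No count is given, and the text available has no eligibility section, so a matching rule elsewhere cannot be excluded. If no pair was mixed, the point has no effect. This also stands; a simple table would settle it.

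Third, retention is only part of surgical trauma. Sectioning depends on position, so concordant pairs can still differ. That is a fair limit on the sensitivity analysis, not a reason to ignore retention.

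A reader might infer something stronger: that the closure estimate is biased. The Study Protocol section does describe suture on the first tooth and adhesive on the second, which conflicts with its own envelope draw. If closure had followed order and the bone-retained tooth had tended to come second, bias would follow. But nothing links retention to order, and the envelope draw is stated in both surgical sections. The order wording needs reconciling as a separate matter. A reader might also take retention type to be a recorded variable. That is a reasonable inference, but the form's contents are described only in general terms.

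**Conclusion.** The point holds as one about precision and chance imbalance. The text allows mixed pairs, describes a bone-removal step for one retention type only, and lists no test that adjusts for it. Assuming 10 of 30 patients are mixed and an effect of 0.5 to 1.0 SD of the within-patient difference, the standard error of an unadjusted paired difference rises by about 4% to 15%. With 6 to 15 mixed patients the range is about 2% to 22%. Both inputs are assumptions. At the lower end the loss is minor, and with no mixed pairs it is nil. The documents do not support a claim of systematic bias from retention.

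**What to change.** Compare closure techniques on swelling and mouth opening with a within-patient model that includes tooth-level retention type (mucosal or bone, as classified before closure). Two forms would serve: a regression of the suture-minus-adhesive difference on the difference in retention, or a mixed model with patient as random effect. This replaces the Student t and Mann-Whitney U tests between groups, which take no covariate and treat the two sides as independent.

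First confirm that retention is among the tooth data on the anamnesis form or can be recovered from the operation record. Tabulate retention by closure technique, with the number of mixed pairs. Report the closure difference in concordant pairs as a sensitivity result only.

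**Cost.**

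- The between-group test changes, which is more than a wording edit.
- One degree of freedom is spent, plus a small loss if the split is uneven. With 10 mixed patients split 7/3, x has mean 4/30 = 0.133 and sum of squares about its mean 10 − 30 × 0.133² = 9.47. The adjusted standard error is then √(1/30 + 0.133²/9.47) = 0.188 SD against 0.183, about 3% more. At the low end of the assumed effect, the net gain is therefore small.
- The concordant set may be much smaller: 30 − 10 = 20 or 30 − 15 = 15 patients if 10 or 15 are mixed.
- The documents are written in the past tense. If the adjustment is added after results were seen, it must be labelled post hoc.

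### No planned analysis uses extraction order, so a first-versus-second operation difference can leak into the closure estimate when the sequences are uneven, or stay in its error when they are even

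*Combined protocol and SAP*

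**What the plan says.** The Study Protocol section gives the size and timing: "A total of 60 lower impacted wisdom teeth were extracted from 30 patients participating in the study", and "One mucosal or bone retention fully impacted wisdom tooth was extracted from each patient at a time". The second side follows later: "The tooth extraction on the other side of the same patient was performed 3 weeks later after postoperative complications were eliminated".

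On allocation the same section says "The wound closure technique to be applied to the tooth to be extracted was randomly decided by the closed envelope method". Surgical Technique and Application adds that "the surgical procedure was completed using a different technique in the other tooth extraction". Together these make a two-period, two-sequence within-patient design, in which the draw for the first tooth settles the closure for both. No allocation ratio, blocking or balancing of order is described.

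Statistical Analyses compares the closures as two groups: "Student t-test was used in quantitative two-group evaluations showing normal distribution", with Mann-Whitney U for non-normal variables and chi-square or Fisher-type tests for categorical ones. Paired and repeated-measures tests appear only for changes over follow-up within a group. Nothing there refers to first or second operation.

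**The concern.** A patient coming to the second operation has been through the first one about 3 weeks before. Experience and expectation can shift pain and other reported outcomes whichever closure is used. If such a period difference exists and the analysis ignores it, one of two things happens. If more patients had one closure first, part of the period difference is counted as closure effect. If the sequences are equal in size, the period difference cancels from the estimate but remains in the residual variance, and the test loses power.

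This is separate from the choice between paired and unpaired tests: a plain paired t-test without order has the same gap.

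**Working it through.** **Inputs from the documents.** 30 patients and 60 teeth, one tooth per closure in each patient; two successive operations; two-group tests at 0.05 (sidedness not stated, two-sided assumed). The documents give no effect size, SD or power, so there is no figure to reproduce beyond 30 × 2 = 60.

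**Assumed, because the documents are silent.** The period effect p (second minus first), the within-patient correlation ρ, the true closure effect, and independent 1:1 envelope draws.

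**Step 1: leak.** Let n1 patients have suture first and n2 adhesive first, and let τ be the true adhesive-minus-suture effect. The expected within-patient difference is τ + p with suture first and τ − p with adhesive first. The unadjusted mean difference is therefore

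τ + p(n1 − n2)/30.

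- 15/15: 0
- 18/12: 6/30 = 20% of p
- 20/10: 10/30 = 33% of p

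**Step 2: how often.** With Binomial(30, 0.5), a split of 18/12 or worse has probability 0.362, and 20/10 or worse 0.099. The expected leak over all draws is zero, and its SD is p/√30 = 0.18p.

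**Step 3: variance at 15/15.** Write p = k × SD of the within-patient difference.

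- A paired test without order estimates a variance larger by the factor 1 + k².
- In the two-group test each group mixes first and second operations half and half, which adds p²/4 to the per-group variance. Since the SD of the difference is √(2(1 − ρ)) outcome SDs, the relative increase is k²(1 − ρ)/2, or k²/4 at ρ = 0.5.

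| k (assumed) | Paired test | Two-group test as planned, ρ = 0.5 |
|---|---|---|
| 0.25 | +6% | +2% |
| 0.5 | +25% | +6% |
| 1.0 | +100% | +25% |

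At k = 0.5 the two-group increase is 0.25 × 0.7/2 = 9% for ρ = 0.3 and 0.25 × 0.3/2 = 4% for ρ = 0.7.

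**Step 4: power and type I error by simulation** (30 patients, 20,000 runs per setting; p and the true effect in outcome SDs). With ρ = 0.5, true effect 0.5 and a 15/15 split:

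| p | Two-group test as planned | Paired, no order | Paired with order |
|---|---|---|---|
| 0.5 | 44% | 67% | 75% |
| 0.8 | 39% | 55% | 75% |

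Averaged over random draws with no closure effect and p = 0.5, type I error is about 5% for the paired test and 0.3–2.8% for the two-group test, which is conservative because it ignores pairing. Given a realised 20/10 split, the paired test without order rejects in 9–12% of runs. With an order term it stays at about 5%, and the estimate is 0.50 for a true 0.50 at 15/15, 18/12 and 20/10.

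**Step 5: price of the order term.** The adjusted estimate is the plain average of the two sequence means, with variance (σ²/4)(1/n1 + 1/n2), where σ² is the variance of the within-patient difference given sequence. At 15/15 this is σ²/30, so nothing is lost but one degree of freedom. At 18/12 it is 0.0347σ² against 0.0333σ² (+4%), and at 20/10 it is 0.0375σ² (+12.5%).

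**The case against.** The strongest objections concern size and reach, and several stand.

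- **Bias.** A reader might infer that the plan biases the closure effect or inflates type I error even under a perfect draw. It does not: over correct draws the estimate is unbiased and type I error is not raised. What remains is chance leak in the realised split and lost precision. The closed-envelope description is also compatible with a fixed 15/15 set, in which case only the precision loss applies.
- **Magnitude.** A reader might take the 100% figure to mean that the plan throws away half its patients. That figure needs a period effect of 1.0 SD, which nothing in the documents supports, and it belongs to a paired test. For the planned two-group test the figure is about 25%. At a period effect of 0.2 outcome SD the variance rises by only 1% in the two-group test and 3–7% in a paired one (ρ from 0.7 down to 0.3 giving the smaller end).
- **Mechanism.** Residual stiffness or swelling cannot be used as an argument: both the Study Protocol and the Surgical Technique sections make healing and restored mouth opening a condition of the second operation. Experience and expectation remain plausible, but their size is unknown.
- **Carry-over.** It is tempting to compare the closure contrast between sequences as a test of whether 3 weeks was long enough. With carry-over λS from suture and λA from adhesive, the contrasts are τ + p + λS and τ − p − λA. Their gap, 2p + λS + λA, mixes period with carry-over, and the differential carry-over λS − λA that would bias τ is absent from it. A period term does not remove that bias either.
- **Relative value.** In the example with p = 0.5, pairing lifts power from 44% to 67% and order adds a further step to 75%. The order term is the smaller gain, but it is a gain of its own.

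**Conclusion.** The point holds in a limited form. The design has two successive operations per patient, and the analysis ignores which came first. The consequence is a leak of 20% of any period difference at 18/12 and 33% at 20/10 (probability 0.36 and 0.10 of a split at least that uneven, if draws are independent 1:1), or, at 15/15, a modest loss of precision in the planned test. Every absolute size depends on a period effect that the documents do not give; if it is small, the gain from adjusting is small.

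One condition comes first. The Study Protocol section also says "In Group 1, a full thickness gingival flap was lifted to reach the first tooth to be extracted" for the sutured group and "in Group 2, the lifted full thickness flap of the second tooth to be extracted was brought to the starting position" for the adhesive group. A reader might infer that every patient had suture first. The documents do not settle this, because the envelope description says otherwise. If that wording were literal (30/0), period could not be separated from closure and no order term could be estimated. With p = 0.5 outcome SD and no closure effect, the false-positive rate would then be about 47% for the two-group test and 61–93% for a paired one.

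**What to change.** 1. Reconcile the first-tooth/second-tooth wording in the Study Protocol section with the envelope description, and state the number of patients in each sequence.
2. Record for each tooth whether it was the first or second extraction, taken from the operation dates (assumed to be on file).
3. Estimate the closure effect within patients with period included: a mixed model with closure and period as fixed effects and patient as random effect, or the two-sequence crossover t-test on within-patient period differences (half the between-sequence difference estimates the closure effect). For non-normal outcomes, use the rank-sum test on those period differences between sequences.
4. Do not present the by-sequence contrast as a check for carry-over.

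The cost is a change of SAP wording, one degree of freedom, and the small variance increase shown above if the split is uneven. No new patients are needed. If the split proves to be 30/0, this fix does not work and the report must say that closure and order are confounded.

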The tension-free wound lips were closed by selecting the wound closure technique with the closed envelope method and providing appropriate procedures. The wound closure technique determined as suture wound closure was determined as the relevant dental control group. After the extraction socket was cleaned and bleeding control was provided, the wound lips were prepared without tension. The surgical site was closed primarily with 3/0, 16 mm 3/8 round needle atraumatic silk sutures. Postoperative recommendations were informed to the patient verbally and in writing. For infection control, 1000 mg amoxicillin+clavunate containing medication was prescribed 2x1 for 5 days. For pain control, 600 mg ibuprofen group analgesic was prescribed and recommended to be used 2x1. Cold compress was recommended for the first 8 hours after the operation for edema control. Appointments were made for the patient to come for the 3rd day and 1-week check-ups after the procedure. When the patient came for the check-up 1 week later, his sutures were removed.

The extraction of the tooth to which cyanoacrylate tissue adhesive would be applied was also performed with the same protocol and the surgical site was closed with cyanoacrylate tissue adhesive (Periacryl 90). While applying the tissue adhesive, the wound site was isolated from blood and saliva with an aspirator and sponge. Periacryl 90 liquid tissue adhesive was dropped onto a sterile perforated tray. Tissue adhesive was drawn into the applicator with a sterile applicator. The wound lips were brought together and the tissue adhesive was applied in a single layer with the applicator. Care was taken to ensure a tension-free closure. After the application, 30 seconds were waited for polymerization. The wound site was checked and the operation was terminated. Appointments were made for the 3rd day and 1-week check-ups after the procedure. It was recommended that the wound site not be traumatized with a toothbrush for 48 hours.

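### Leaving out patients whose extraction sites did not heal is, as written, an exclusion after allocation on a result the closure can affect, and no exclusion numbers are given

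*Combined protocol and SAP*

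**What the plan says.** The Study Protocol section reports the size of the trial: "A total of 60 lower impacted wisdom teeth were extracted from 30 patients participating in the study". The second side was "performed 3 weeks later after postoperative complications were eliminated and the extraction site wound healed and the mouth opening returned to its previous value". The next sentence is the rule at issue: "Patients whose extraction sites did not heal were not included in the study".

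The Surgical Technique and Application section repeats the condition for the second extraction ("The tooth extraction on the other side was performed after the postoperative complications were eliminated and the extraction site wound healed") without any exclusion. It places the envelope draw at wound closure: "The tension-free wound lips were closed by selecting the wound closure technique with the closed envelope method". It also says that "the surgical procedure was completed using a different technique in the other tooth extraction", so one draw settles the closure of both teeth. Follow-up is described as "Appointments were made for the patient to come for the 3rd day and 1-week check-ups after the procedure".

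The Statistical Analyses section names no analysis population and says nothing about patients left out or pairs left incomplete.

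**The concern.** A baseline eligibility criterion cannot be affected by treatment. This rule can be. A site can fail to heal only once the tooth is out and the wound is closed, and the trial compares two ways of closing it. Read literally, the rule removes the whole patient because of what happened on an allocated side, so the within-patient design gives no protection. First-tooth results from day 3 and week 1 would probably go too, although the document does not say so.

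All 30 reported patients are completed pairs, so any first-tooth failure that led to removal would be invisible. If anyone was removed, the teeth compared are those selected for having healed. A difference in non-healing would then be distorted or erased, and outcomes correlated with healing could shift as well.

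**Working it through.** **Count check.** 30 patients × 2 teeth = 60 teeth, as reported. Every reported patient therefore has both sides treated. The document gives no power calculation, event rate, number allocated or number excluded, so everything below rests on assumed rates. Non-healing is not a named endpoint.

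**Notation.** g and s are the true non-healing rates with adhesive and suture, and b is the probability that both sites fail in one patient. Differences are adhesive minus suture.

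**Reading 1: random order (50:50), patient removed if the first site fails.**
- Share kept: T = 1 − (g + s)/2.
- Observed rates: adhesive 0.5(g − b)/T, suture 0.5(s − b)/T.
- Observed risk difference: (g − s)/(2 − g − s). It does not depend on b, so the correlation between sites does not matter.
- Removals implied by 30 completed pairs: 30/T − 30.

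| Assumed g v s | True difference (points) | Observed difference | Implied removals |
|---|---|---|---|
| 5% v 1% | 4.0 | 0.04/1.94 = 2.1 | 30/0.97 − 30 = 0.9 |
| 10% v 2% | 8.0 | 0.08/1.88 = 4.3 | 30/0.94 − 30 = 1.9 |
| 20% v 5% | 15.0 | 0.15/1.75 = 8.6 | 30/0.875 − 30 = 4.3 |
| 5% v 15% | −10.0 | −0.10/1.80 = −5.6 | 30/0.90 − 30 = 3.3 |
| 10% v 10% | 0 | 0 | 30/0.90 − 30 = 3.3 |

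The risk ratio, (g − b)/(s − b), moves the other way, away from 1:
- Independent sites (b = gs): at 10% v 2%, 0.098/0.018 = 5.44 against a true 5.0. At 20% v 5%, 0.19/0.04 = 4.75 against a true 4.0.
- Latent correlation 0.5 between sites (b = 0.0093 and 0.0292): 8.51 and 8.21, computed before rounding b.

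**Reading 2: patient removed if either site fails.** Observed non-healing is 0 in both groups, whatever the truth.

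**Reading 3: first-site rule with suture always first.** The Study Protocol section also ties suture to the first tooth and adhesive to the second, which conflicts with the envelope draw. On that order, observed suture non-healing is 0 and observed adhesive non-healing is (g − b)/(1 − s).
- 10% v 10%: a false difference of 10 points with independent sites (0.09/0.90), or 7.5 points at latent correlation 0.5.
- 5% v 15%: the true −10 points becomes +5 (independent sites) or about +3 (latent correlation 0.5), so the sign changes.

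**Continuous outcome, no true difference.** Simulation of 2,000,000 patients per scenario, rates 10% v 2%, 20% v 5%, 5% v 15% and 10% v 10%. Higher values are worse, the correlation with failure to heal is 0.3 to 0.6, and the within-patient correlation is 0 to 0.5.
- First-site rule, random order: bias −0.06 to +0.04 SD.
- Either-site rule: −0.15 to +0.10 SD. The extremes need a correlation of 0.6 with failure and no within-patient correlation. At within-patient correlation 0.5 the range is about −0.08 to +0.05 SD.
- Equal rates under either of these rules: 0.
- Suture always first, first-site rule: up to about +0.16 SD.
- For comparison, the standard error for 30 v 30 unpaired teeth is √(2/30) = 0.26 SD. For pairs with correlation 0.5 it is √(2 × 0.5/30) = 0.18 SD.

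**Chance that nobody was removed among 30 allocated patients**, (1 − p)^30 with p the average first-site rate: 74% at 1%, 55% at 2%, 16% at 6%.

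**Does keeping first teeth repair it?** With random order and all first teeth kept, the rates are (2g − b)/(2 − s) for adhesive and (2s − b)/(2 − g) for suture. The difference returns to 8.0 points at 10% v 2% and to 15.0–15.1 points at 20% v 5%. For a continuous outcome with within-patient correlation 0.5, simple means of the kept teeth still differ by −0.02 to +0.03 SD, which is why the model needs a patient effect.

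**The case against.** The strongest reply is that the sentence was never an analysis rule. It directly follows the condition for the second extraction and may only restate it, and the surgical section repeats that condition with no exclusion. This reading is possible. But the condition had already been stated, and the sentence speaks of inclusion in the study, not of the second operation. Even on this reading, patients who never reached the second side are absent from 30 completed pairs, so the same selection arises if there were any such patients.

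No exclusion is shown, and at low failure rates none is the likeliest outcome. This stands, and it is why the concern is conditional.

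The largest effects concern non-healing, which is not a named endpoint. Mouth opening appears only as a preoperative measurement and as part of the condition for the second side, so its use as an outcome is an inference. For continuous outcomes the modelled bias is below one standard error. All of this stands and limits the weight of the point.

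Finally, exclusion counts belong in a results report. That is fair, but the plan-level gap remains: a stated rule that selects on healing, no analysis population, and no handling of incomplete pairs.

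**Conclusion.** The concern holds. As written, the rule acts after allocation on a result that the closure can affect, and nothing elsewhere in the document resolves it. It should be fixed. Confidence is medium, because the actual effect is unknown and is nil if nobody was removed.

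Under assumed rates with random order and a first-site rule, a non-healing difference shrinks to a little over half its true size, while the risk ratio is exaggerated. An either-site rule erases non-healing from the comparison altogether. Bias in continuous outcomes is probably small and can take either sign. These figures for the first-site rule assume random order. If suture was always first, that rule could create a difference where none exists or reverse a true one. The contradiction about order is a separate matter, but it must be reconciled before either the direction or the size can be stated for this trial.

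**What to change.** First, state what the sentence meant: whether it covered the first site or either site, and how and when non-healing was judged. Report the numbers allocated and left out by closure, order and reason, or state that none were left out. If the sentence was only a condition on the second operation, say so.

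Then set the analysis accordingly:
- Do not use non-healing as a reason for exclusion from the analysis. Leave the clinical condition for the second extraction unchanged.
- Analyse every allocated patient by allocated closure.
- Keep first-tooth data where there was no second extraction, using a method that accepts unpaired teeth, such as a mixed model with a patient effect.
- Count non-healing by closure, with a stated definition and time point.
- Show the completed pairs as a sensitivity analysis.

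If nobody was left out, the statement of that fact settles this point. Otherwise the cost is analysis and reporting text, some record retrieval and a slightly more complex model. Complication rates may look less favourable once the omitted patients are counted.
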